3.1 Overview of the Study Design

This study has been designed in accordance with the *Declaration of Helsinki*.³⁴

This is a phase 4, interventional, multi-national, multi-site, randomized, double-blind, parallel-group, placebo-controlled study designed to demonstrate the efficacy and safety of add-on eptinezumab treatment to BI, performed at baseline, for the prevention of migraine and treatment of MOH in patients with a dual diagnosis of migraine and MOH.

The 12-week placebo-controlled period will be followed by a 12-week open-label period where all patients will receive eptinezumab to provide further relief and gain exploratory data on the durability of a potential remission of the MOH and CM. The safety and tolerability of eptinezumab will be also further assessed in this open-label period.

This study will be conducted in compliance with the protocol, *Good Clinical Practice*,³⁵ and applicable regulatory requirements.

An overview of the study is presented in [Panel 1](#).

The target population for this study is defined as patients with a dual diagnosis of migraine and MOH and a level of disease activity matching the CM definition, according to the IHS ICHD-3 guidelines.¹ The medication overuse will be confirmed via prospectively collected information in the eDiary during the screening period.

Patients will be instructed to stop medication overuse during a semi-structured educational conversation.

Patients will be allowed use of medications (with restrictions for some of them) for acute and/or symptomatic treatment of headache (for example, paracetamol, NSAID, triptans, ergotamine, opioids, and/or combination analgesics) throughout the study. However, at the Baseline Visit they will be educated not to use acute medications.

Eligible patients will be randomly allocated via a randomization system to one of the two treatment groups: BI and eptinezumab 100 mg, or BI and placebo, in a ratio of 1:1.

Randomization will be stratified by country and number of previous preventive treatment failures (≤ 2 ; > 2) occurring up to 5 years prior to Baseline Visit by using the IRT system. Treatment failure is defined as treatment discontinuation due to lack of efficacy (no clinically meaningful improvement at the recommended or prescribed dose for at least 3 months), side effects, or general poor tolerability of the treatment.

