11.5 Analysis of Secondary Endpoints

For the Placebo-controlled Period, the secondary endpoints will be summarized by treatment group based on the FAS. For the Open-label Period, the secondary endpoints will be summarized by treatment sequence based on the APTS-OL.

For analyses related to eDiary, estimands follow the same rationale and strategies to address intercurrent events in Section 11.3.1 for continuous endpoints or Section 11.3.1. for binary endpoints in Placebo-controlled Period.

- Migraine on the day after dosing (Day 1) will be derived according to the descriptions in Section 15.1.3 and will be analysed using an extended Cochran-Mantel-Haenszel (CMH) test, adjusting for country and previous treatment failures (≤ 2 , > 2). The estimated proportions for EPTI and PBO will be presented.

The following binary endpoints for the Placebo-controlled Period will be analysed using logistic regression test including country and previous treatment failures as stratification variables (where the stratification variables will indicate the strata used for randomisation), similar to the one used in key secondary analysis in the not fulfilling the ICHD-3 diagnostic criteria for CM nor MOH endpoint.

- Not fulfilling the ICHD-3 diagnostic criteria for CM (Weeks 1-4, Weeks 1-12)
- Not fulfilling the ICHD-3 diagnostic criteria for MOH (Weeks 1-4, Weeks 1-12)
- Not fulfilling the ICHD-3 diagnostic criteria for CM nor MOH (Weeks 13-24) (Only descriptive summaries)

The following continuous endpoints for the Placebo-controlled Period will be analysed using an MMRM model similar to the one used for primary analysis and key secondary analysis, the baseline MMD score will be replaced with the baseline score for the corresponding endpoint in the model.

- Change from baseline in MMDs with use of acute migraine medication (Weeks 1-12)
- Change from baseline in monthly days with triptan or ergotamine medication use (Weeks 1-12)
- Change from baseline in monthly days with individual non-opioid analgesics or NSAID medication use (Weeks 1-12)
- Change from baseline in monthly days with combination non-opioid analgesics medication use (Weeks 1-12)

- Change from baseline in rate of migraines with severe pain intensity (Weeks 1-4, Weeks 1-12)
- Change from baseline in rate of headaches with severe pain intensity (Weeks 1-4, Week 1-12)
- Change from baseline to Weeks 13-24 in MMDs (Only descriptive summaries)

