- TSQM-9 score at Week 4 and Week 12 (Effectiveness, Convenience, Overall Satisfaction) (exclude baseline covariate in the model)
- PGIC score at Week 4 and Week 12 (exclude baseline covariate in the model)

The endpoint based on MBS scores test between EPTI and PBO at Week12 will use similar ANCOVA model defined in the analysis of key secondary endpoint: change from baseline in average Daily Pain assessment score.

- MBS score at Week 12 (exclude baseline covariate in the model)

The following endpoints based on diary data and health-related quality of life scores between EPTI-EPTI and PBO-EPTI will be summarized by descriptive tables.

- Change from baseline to Week 24 in average Daily Pain assessment score
- Change from baseline to Week 24 in the HIT-6 total score
- Change from baseline to Week 24 in the mMIDAS total score
- Change from baseline to Week 24 in the MSQ v2.1 sub-scores
- Change from baseline to Week 24 in the EQ-5D-5L VAS score
- Change from baseline to Week 24 in the WPAI:M sub-scores
- Change from baseline to Week 24 in HADS sub-scores
- TSQM-9 sub-scores at Week 24
- PGIC score at Week 24
- MBS score at Week 24

Descriptive tables displaying the distribution of answers to the items in HCRU at each visit will be provided by treatment group.

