12.4 Other Safety Endpoints

12.4.1 Screening Assessments

Clinical laboratory, ECG, reproductive system, physical and neurological examinations are performed at screening. Any abnormal finding or out-of-range value considered clinically significant by the investigator will be recorded as an adverse event on an *Adverse Event Form*.

The Columbia-Suicide Severity Rating Scale (C-SSRS)³ is a semi-structured interview developed to systematically assess suicidal ideation and behaviour of participants participating in a clinical trial. The C-SSRS has 5 questions addressing suicidal ideation, 5 sub-questions assessing the intensity of ideation, and 4 questions addressing suicidal behaviour. For this trial, the following versions of the scale are used: the “Baseline/Screening” version (lifetime and 1 year assessment).

Table 5 C-SSRS Scores

C-SSRS Score	Related to:
1 Wish to be dead	Suicidal ideation
2 Non-specific active suicidal thoughts	
3 Active suicidal ideation with any methods (not plan) without intent to act	
4 Active suicidal ideation with some intent to act, without specific plan	
5 Active suicidal ideation with specific plan and intent	
6 Preparatory acts or behaviour	Suicidal behaviour
7 Aborted attempt	
8 Interrupted attempt	
9 Non-fatal suicide attempt	
10 Completed suicide (only applicable for the post-baseline assessments)	

13 Interim Analysis

No interim analysis is planned.

14 Sample Size Considerations

The sample size calculation assumes that the treatment effect of eptinezumab 100 mg compared to placebo in change from baseline in MMDs (Weeks 1 to 4) will be -1.5 MMDs. The difference between eptinezumab 100 mg and placebo was -2.0 in Study 011, a trial that did not include education on MOH, after 4 weeks and -3.1 in the subgroup of participants with CM and MOH. The difference between withdrawal from treatment with and without preventive treatment was -1.7 and -1.4 days after 2 and 4 months. The SD is assumed to be 6.2, based on the averaged SD

across treatment groups in the MOH subgroup of Study 011 on the change from baseline in MMDs (Weeks 1 to 4).

Based on the assumed effect size and SD, using a two-sided test on the 5% significance level, 270 participants per treatment group will provide 80% power for showing an effect on the primary endpoint. Assuming that 5% of participants will not contribute data to the analysis. 285 participants randomized per treatment group, or 570 participants randomized in total will be needed.

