18.5.4 Binary Endpoints

A logistic regression model will be used for all the binary endpoints, except “Migraine on the day after dosing” (in accordance with protocol synopsis, but not protocol body).

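### The Day 1 migraine analysis leaves out baseline MMDs and specifies no confidence interval for the treatment difference: a valid test, with a small gain in precision available at almost no cost

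*SAP*

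**What the plan says.** For the Day 1 endpoint, SAP 11.5 says that it "will be analysed using an extended Cochran-Mantel-Haenszel (CMH) test, adjusting for country and previous treatment failures", and that the estimated proportions for the two groups will be shown. No treatment difference or interval is specified. SAP 18.5.4 records the exception among the changes to the protocol: "A logistic regression model will be used for all the binary endpoints, except" this one. It gives no reason.

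The other binary endpoints from the diary are handled differently. The CM/MOH endpoints (SAP 11.4.2 and 11.5) use logistic regression with baseline MMDs, country and previous treatment failures. The 50% and 75% responder endpoints use baseline MMDs or MHDs in the same way, with odds ratios and profile-likelihood intervals. SAP 11.4.3 explains that baseline MMDs are included because they predict response.

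Three further provisions matter:

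- Baseline MMDs come from the 28-day screening diary (SAP 3.1), and membership of the FAS requires a valid baseline (SAP section 4).
- A missing Day 1 diary is replaced by 100 × (Weeks 1-4 MMDs)/28 (SAP 15.1.3), so the outcome can be a fraction as well as 0 or 100.
- The nine-step hierarchy in SAP 11.2 does not include the Day 1 endpoint.

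PGIC, TSQM-9 and MBS also carry no baseline term, for example "PGIC score at Week 4 and Week 12 (exclude baseline covariate in the model".

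**The concern.** A participant's chance of migraine on any given day depends directly on how often that participant has migraine. Eligibility requires at least 8 migraine days and at most 26 headache days in screening (Protocol 9.1.3), so baseline MMD/28 can run from 8/28 = 0.29 to 26/28 = 0.93. Ignoring that spread leaves explainable variation in the error term. The SAP's own reason for adjusting the other binary endpoints applies at least as strongly here.

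The second gap is reporting. A p-value and two proportions give the reader a difference by subtraction but no measure of its uncertainty. At stake are the precision and readability of one secondary result, the only one that looks at a single day after the infusion. No confirmatory claim depends on it.

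**Working it through.** **The plan's own figure.** SAP section 14 sizes the trial on the primary endpoint only: a treatment effect "in change from baseline in MMDs (Weeks 1 to 4) will be -1.5 MMDs", "The SD is assumed to be 6.2", and "using a two-sided test on the 5% significance level, 270 participants per treatment group will provide 80% power". The formula gives n = 2 × (1.960 + 0.842)² × 6.2²/1.5² = 268.2, so 269 per group. With 270 per group the power is 80.3%. Allowing for 5% non-contributors, 270/0.95 = 284.2, so 285 per group and 570 in total. The figure reproduces. It is unaffected by this point, because the primary model already contains baseline MMDs. No power figure is given for Day 1. I use the 270 per group below.

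**Assumptions not in the documents.** Baseline MMD mean m and SD s; Day 1 placebo risk p₀ = k × m/28; 10-point difference, so p₁ = p₀ − 0.10.

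**Formulas.** Variance explained by baseline: v = (k × s/28)². As a share of the outcome variance: R² = v/[p₀(1 − p₀)]. Standard error without adjustment: √{[p₀(1 − p₀) + p₁(1 − p₁)]/270}. With adjustment, subtract 2v from the bracket. Power = Φ(0.10/SE − 1.96).

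**Worked case (m = 19, s = 4.5, k = 0.85).** p₀ = 0.577 and p₁ = 0.477. v = (0.85 × 4.5/28)² = 0.0187. R² = 0.0187/0.2441 = 0.076. SE without adjustment = √[(0.2441 + 0.2495)/270] = 0.0428, power 65%. SE with adjustment = √[(0.4936 − 0.0373)/270] = 0.0411, power 68%. Simulation of 4000 trials with these inputs gave the same 65% and 68%, with a variance ratio of about 0.93.

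**Other inputs, same formulas:**

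| m | s | k | R² | Power unadjusted | Power adjusted |
|---|---|---|---|---|---|
| 17 | 4 | 0.75 | 0.046 | 66% | 68% |
| 17 | 4 | 1.0 | 0.086 | 65% | 69% |
| 19 | 4.5 | 1.0 | 0.118 | 68% | 73% |

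These closed forms let baseline range freely. Eligibility cuts it to 8-26 days, which shrinks its variance and the gain. Simulating the planned stratified mean-score CMH test against the adjusted linear model, with baseline held to 8-26 days and the same range of inputs, gives a gain of about 2-4 power points, with type I error at 5%.

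**Wider inputs.** With a 12-point difference, mean 17, SD 3-5.2 and k = 0.75-1.0, the SE falls by 1-6%. Power moves from 81.0% to 81.8% in the least favourable case and from 78.5% to 84.1% in the most favourable. With no true difference (SD 4, k = 1.0), rejection rates were 0.051 unadjusted and 0.049 adjusted.

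**PGIC, TSQM-9 and MBS.** Residual variance falls by the factor 1 − r², where r is the correlation with baseline MMDs. The documents do not give r. Starting from 80% power, r = 0.1 gives 80.4%, r = 0.2 gives 81.6% and r = 0.3 gives 83.6%.

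**The case against.** The strongest reply is that nothing is wrong with the planned test. Randomisation makes the stratified CMH valid without the covariate, and the simulated error rate confirms it. The choice is also deliberate and rooted in the protocol: Protocol 16.8.7 specifies CMH for binary secondary endpoints, and the SAP adds country and declares the exception. A reason can be inferred although it is not stated: the fractional imputed values of SAP 15.1.3 do not fit ordinary logistic regression. The gain rests on inputs that the documents do not supply, and no confirmatory conclusion can change. All of this stands, and it is why the point is low in severity and why the CMH p-value should be kept. It does not explain leaving out the covariate, since a linear model on the 0-100 rate accepts fractions.

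A reader might infer three stronger things that the documents do not support:

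- **That Day 1 is the plan's only test of onset.** It is the only single-day test. Average Daily Pain over Weeks 1-2 is a key secondary endpoint (SAP 11.2, Step 7), analysed by ANCOVA with baseline pain and reported with a 95% CI.
- **That the plan gives no effect information for Day 1.** The two proportions are presented. What is missing is an interval for their difference.
- **That dropping the baseline term wastes precision for PGIC and TSQM-9.** Neither has a usable baseline of its own: PGIC rates change since the Baseline Visit (SAP 15.4), and the baseline TSQM-9 is only practice (SAP 18.2). Baseline MMDs could stand in, but the gain may be near zero.

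**Conclusion.** The point holds as a low-severity improvement to efficiency and reporting. The Day 1 analysis omits a covariate that every FAS participant has and that the SAP itself treats as predictive, and it specifies no interval for the treatment difference. Under the assumed inputs (baseline MMD mean 17-19, SD 4-4.5, k = 0.75-1.0, 10-point difference, 270 per group), adjustment is worth about 2-4 power points and leaves type I error at 5%. That size depends on those assumptions; the missing interval does not. The finding implies no bias in the planned test and leaves the primary endpoint, the hierarchy and the sample size untouched.

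**What to change.** In SAP 11.5, specify for the Day 1 endpoint a linear model of the 0-100 rate, including the fractional imputed values of 15.1.3, with treatment, country, previous treatment failures and baseline MMDs, and robust standard errors. Report the treatment difference in percentage points with its 95% CI. Keep the CMH p-value alongside as the protocol-based test, and amend SAP 18.5.4 to match.

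Timing needs care. SAP version 3.0 already takes in the classification meeting, and SAP section 4 places unblinding after that meeting. If unblinding has occurred, label the adjusted analysis as supportive.

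Baseline MMDs in the PGIC, TSQM-9 and MBS models are optional; if they are added, treat all three alike.

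The cost is a short SAP amendment and one simple model, close to the Daily Pain ANCOVA already specified but with a different covariate and robust standard errors. No new data are needed.

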11.6 Analysis of Exploratory Endpoints

Analysis of exploratory endpoints for primary efficacy objectives will be based on FAS. For the Open-label Period, the exploratory endpoints will be summarized by treatment sequence based on the APTS-OL.

For analyses related to eDiary, estimands follow the same rationale and strategies to address intercurrent events in Section 11.3.1 for continuous endpoints or Section 11.4.1. for binary endpoints in Placebo-controlled Period.

- Complete withdrawal of acute headache medication (Weeks 1-4, Weeks 5-8, Weeks 9-12)

Participants completely withdrawn of acute headache medication is defined as the participants doesn't take any acute migraine medication during the 4-week interval period of interest.

Complete withdrawal of acute headache medication will be analysed using logistic regression including country and previous treatment failures as stratification variables (where the stratification variables will indicate the strata used for randomisation), similar to the one used in key secondary analysis in the not fulfilling the ICHD-3 diagnostic criteria for CM nor MOH endpoint.

To investigate the efficacy of eptinezumab as add-on to BI on level of daily physical activity and sleep using a wearable digital device (subset), the following continuous endpoints will be summarized:

- Change from baseline to Week 1-4 and Week 1-12 of passive registration of movement (actigraphy) (average per 28 days)
 - Number of average total minutes in no motion (0 - <10 a.U.)
 - Number of average total minutes with light motion (10 - <50 a.U.)
 - Number of average total minutes with moderate motion (50 - <100 a.U.)
 - Number of average total minutes with vigorous motion (\geq 100 a.U.)
- Change from baseline to Week 1-4 and Week 1-12 in sleep metrics assessment as assessed by actigraphy (average per 28 days)
 - Number of average total minutes of Total Sleep Time
 - Average proportion of Effective Sleep
 - Number of average total minutes of Wake After Sleep Onset
 - Number of average total minutes of Sleep Onset Latency

All analyses will also be done by week, for example change from baseline to Week 1, baseline to Week 2, and until baseline to Week 12.

To investigate the efficacy of eptinezumab as add-on to BI on level of analgesic dependence, change from baseline to Week 12 in SDS:H score will be analysed using an ANCOVA model similar to the one used for key secondary analysis.

- Change from baseline to Week 12 in SDS:H score

The number of days with auras without headache is derived based on the information in the aura without headache eDiary. The endpoint will be analysed in the subgroup of FAS participants which are diagnosed as migraine participants with aura at baseline as per the doctor's diagnosis in the eCRF. The change from baseline in number of days with auras without headache for the Placebo-controlled Period will be analysed using an MMRM model similar to the one used for primary analysis and key secondary analysis, the baseline MMD score will be replaced with the baseline number of days with auras without headache in the model.

- Change from baseline in number of days with auras without headache (Weeks 1-4, Weeks 1-12, Weeks 13-24) (Only descriptive summaries for Weeks 13-24)

The change from baseline in duration of severe pain continuous endpoint for the Placebo-controlled Period will be analysed using an MMRM model similar to the one used for primary analysis and key secondary analysis, the baseline MMD score will be replaced with the baseline duration of severe pain in the model.

- Change from baseline in duration of severe pain (Weeks 1-4, Weeks 1-12, Weeks 13-24) (Only descriptive summaries for Weeks 13-24)

The duration of severe pain is derived based on the collected information in the headache eDiary via the question "*What was the worst pain intensity of this headache today?*". For the relevant time period, for all headaches during that period, the duration of severe pain should be summed up over all days on which severe pain ever occurred. If more than 14 days are reported eDiary days, then the number of days with severe pain are calculated based on these days and this

number is prorated. If less than 14 days are reported eDiary days, then the number of days with severe pain will be set to missing.

12 Safety

12.1 Adverse Events

12.1.1 General Methodology for Adverse Events

Unless otherwise specified, tables, graphs, and listings will be based on the APTS for the Placebo-controlled Period and the APTS-OL for the Open-label Period.

All the tables and graphs will be presented by treatment group for the Placebo-controlled Period and by treatment sequence group for the Open-label Period, unless otherwise specified.

Tables by preferred term and tables by SOC and preferred term will be sorted in descending order based on the percentages of participants with these adverse events in EPTI-EPTI or PBO-EPTI group.

Unless otherwise specified, the summaries of adverse events will include the number and percentage of participants with an adverse event. In tables displaying SOC or preferred terms, participants are counted only once within each SOC or preferred term.

Listings of adverse events will be sorted by treatment group including participant ID with site ID, Age, Sex, Race, AE number, SOC/PT/investigator term, AE start date/time, AE stop date/time/ongoing, date of first IMP infusion, date of the latest IMP infusion prior to the adverse event, time since latest IMP infusion, duration of the adverse event, frequency type (continuous/Intermittent), intensity, seriousness, relationship to IMP (Probable/Possible/Not Related: Specify), action taken with IMP and outcome. For adverse events that change in intensity, each intensity will be included. In listings of adverse events, start or stop dates will be displayed as collected also in case of partially or completely missing dates.

All adverse events will be coded using MedDRA, Version 25.0 or later.

12.1.2 Classification of Adverse Events

Adverse events will be classified according to the time of onset of the adverse event:

pre-treatment adverse event – an adverse event that starts on or after the date the participant signed the *Informed Consent Form* and prior to the date and time of first dose of IMP

treatment-emergent adverse event (TEAE) – an adverse event that starts during or after administration of the first dose of IMP, or a pre-treatment adverse event that increases in intensity or becomes serious during or after administration of the first dose of IMP

For handling of adverse events with incomplete start dates to facilitate this classification, see Section 15.14.3. Note that adverse events with incomplete start dates will be classified as treatment-emergent simply if the imputed start date is on or after the date of first IMP infusion, since the start time of the adverse event will not be imputed, unless the investigator in such a case has assessed that the causality to IMP is “Not Related - Prior to IMP”.

An adverse event is considered causally related to the use of the IMP when the causality assessment by the investigator is probable or possible. If the causality assessment is missing, the adverse event is considered causally related.

